Setting: The outpatient treatment center at the UF Health Cancer Center-Orlando will be the primary site for enrollment due to its long-standing relationship with these researchers. In 2013, UF Health Cancer Center-Orlando saw approximately 4,694 patients. Of these 2,573 patients were age 65 or older, and 565 of these patients received outpatient chemotherapy. These numbers indicate an ample sampling pool of older adults.

Sample size: The target sample is older adults receiving emetogenic chemotherapy for the first time. Sixty-six participants will be enrolled if they meet the following **inclusion criteria**: age 65 and older, newly diagnosed with any cancer, treatment with any chemotherapeutic agent with a moderate to severe emetic potential (on a 3- or 4- week cycle), proficient in English, and have a telephone. **Exclusion criteria** include: previous diagnosis and treatment for cancer, advanced or end stage disease with a palliative intent, visually or hearing impaired. Dementia or cognitive impairment is not a concern with the population since they have already been cognitively screened in order to consent to treatment at this cancer center. There will be no exclusion based on gender or racial/ethnic status. Retention of all participants will be enhanced by the following strategies 1) weekly telephone follow-up phone calls by the RA; 2) a \$50 incentive/gift card at the end of the study period; and 3) attention control group offered eSSET-CINV at the end of the study. We will oversample by 20% in order to account for attrition.

Phase II Procedures:

Recruitment and randomization: Successful recruitment and retention strategies previously established by the team will be used during this phase.^{7, 15, 16, 18, 90} Convenience sampling, followed by randomization will be used. All new patients will be screened for eligibility by the Research Nurse (RN-PG) using the Sunrise XA -

electronic medical record system used by Orlando Health. Eligible patients will be approached by the RN at their first chemotherapy appointment and asked to participate. This timing is not expected to add to or create patient anxiety. Patients usually wait 30 to 60 minutes for lab results and chemotherapy to be delivered. Participating

Table 1: Intervention schema

	Pre-treatment		First Treatment Visit			Post - treatment

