Participant characteristics: Demographic and experiential characteristics that may influence CINV and ability to self-manage this symptom will be measured at T1 (baseline). Demographics include: age, gender, comorbidity information, education level, and income level. Experiential characteristics include: cancer diagnosis and stage, chemotherapy regimen with antiemetics, discharge antiemetic prescriptions, use of the Internet to research symptom management information, and caregiver presence (yes/no) and involvement at home. All cancer information will be collected from the patient's electronic medical record by the RN. Delays in chemotherapy treatment and rationale for delay will also be recorded at each time point by the RN.

Dependent Variables

An overview of study variables, measures and data collection timeline are presented in Table 3. Data will be collected for 4 treatment cycles (3 or 4 months depending on cycle length). Questionnaires will use a paper/pencil format with enlarged font and be entered into Excel™ software.

1) Symptom severity: The *Symptom Representation Questionnaire (SRQ)*⁹¹, a 24-item self-report measure will be used to identify presence and severity of common treatment-related symptoms (0-10 Likert scale), including nausea and vomiting (N/V). This measure asks respondents to think about their symptoms over the past week.

Table 2: eSSET-CINV Intervention process

1	Game introduction and orientation
2	Choose avatar
3	Avatar discharged home after treatment
4	Avatar begins to experience nausea
5	Player makes self-management decisions
6	Avatar responds based on player decisions
7	Avatar experience continues with periodic nausea as player continues to make self-management decisions
8	Game ends when avatar achieves goal of mild or no nausea or has an unplanned ED or hospital admission
9	Discussion of decision choices with Research Nurse

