Preliminary data analysis: Descriptive statistics will be provided to characterize the study participants for all demographic and experiential variables at baseline and at each treatment cycle time point. Summary tables will be provided to present participant characteristics (e.g., gender, age group, race), major study variables, game appeal, and willingness to recommend game to others. Internal consistency of study measures will be checked and evaluated to ensure data quality. Effort will be taken as much as possible to avoid missing data. If there are significant missing data that may impact analysis results, the multiple imputation method may be used for the analysis of primary endpoint. All statistical analyses will be performed using Statistical Application Packages (SAS®), version 9.4.

Principle data analysis: The primary endpoints for the study are N/V severity score and the number of self-management behaviors. The secondary endpoints are ED/hospital admission and QOL. Summary statistics for the primary and secondary endpoints will be provided. The t-test will be used if the normality of the endpoint can be confirmed. Otherwise, the Wilcoxon Rank-Sum test will be used to assess the difference between the two groups at each treatment cycle time point.

AIM 1: Estimate effect size of the eSSET-CINV in changing patient outcomes: cognitive representation, self-management behaviors, CINV severity, QOL, and resource use. The effect size of N/V severity score will be estimated using the Cohen’s d, which is defined as the difference between two means divided by a standard deviation for the data.

AIM 2: Examine differences in cognitive representation, self-management behaviors, CINV severity, QOL, and resource use, between, and within, the intervention and attention control groups. For the primary endpoints, the data will be collected over 4 treatment cycles, and the method of analysis of longitudinal data will be used to compare the difference between intervention and control groups over time. The generalized estimating equation (GEE) approach may be used to enhance the robustness of the estimation of model parameters when the ideal working correlation structure is difficult to pre-specify. In the longitudinal model treatment cycle time, interaction of time and treatment, or both, whenever feasible, may be added into the model to assess the time effect on treatment difference.

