The one-way repeated measures ANOVA will be used to assess the difference between the two groups. The mixed effect model may be used as exploratory analysis to account for unobservable variations from each individual patient. In addition, comparisons between two groups at each treatment cycle time point will be performed for all primary and secondary endpoints. For this particular comparison, the univariate normality of each endpoint will be assessed graphically at each treatment cycle time point. An appropriate time window will be determined to define the treatment cycles for the study.

AIM 3: Obtain preliminary data regarding the feasibility and acceptability of the game in older adults experiencing CINV. Feasibility- Computer science and digital media undergraduate students will work under the direction of [name] and [name] to identify patterns in game play data (e.g., self-management decisions, scenario patterns of progression), time to game completion, and number of times the game was played (intervention dose). The RN will track any instance of game play interruptions or

malfuction. This data will be summarized with descriptive statistics. **Game Appeal:** Responses to the game appeal and willingness to recommend questions will be scored and summed using descriptive statistics. Additional comments about the game will be recorded and analyzed for themes.

Sample size and statistical power:

Based on the assumption of a nausea severity mean score of 6.20, range from 2 to 9, a standard deviation of 2.44, and a clinically meaningful difference in mean nausea severity score of one between the intervention and control groups, with 90% power, the required sample size is 33 participants for each group, yielding a total sample size of 66 for the study. To reduce the patient selection bias, single-blinded randomization may be used whenever feasible. Due to lack of available data from prior research the sample size for secondary endpoints is not possible for the study at first stage. However, the power statistical analysis will be assessed when data become available from the planned study.

Potential challenges and strategies for addressing:

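### The covariates recorded at T1 enter no specified between-group analysis, which costs precision and accuracy given whatever imbalance occurs

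*Combined protocol and SAP*

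**What the plan says.** The Co-variates section states that "Demographic and experiential characteristics that may influence CINV and ability to self-manage this symptom will be measured at T1 (baseline". Its list covers age, gender, comorbidity, education and income, then diagnosis and stage, the chemotherapy regimen with its antiemetics, discharge antiemetics, internet use and caregiver presence. Table 3 also schedules symptom severity at T1. Under Recruitment and randomization, baseline measures come before allocation, and allocation is by choosing an envelope, with no stratification stated. Eligibility is broad: any cancer, and "treatment with any chemotherapeutic agent with a moderate to severe emetic potential".

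The Phase II data analysis section names two primary endpoints, N/V severity and the number of self-management behaviors. The group comparisons it describes are:

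- **Principle data analysis:** a t-test at each cycle if normality holds; otherwise "the Wilcoxon Rank-Sum test will be used to assess the difference between the two groups at each treatment cycle time point".
- **AIM 1:** Cohen's d for severity, from two raw means and a standard deviation.
- **AIM 2, longitudinal:** a longitudinal method, possibly GEE, in which "treatment cycle time, interaction of time and treatment, or both, whenever feasible, may be added into the model".
- **AIM 2, other:** a one-way repeated-measures ANOVA, and an exploratory mixed model aimed at unobserved patient variation.

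The T1 characteristics reappear only in the descriptive summaries. The one other planned use of a recorded factor is a subgroup analysis of caregiver involvement in game play.

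**The concern.** A plan that labels variables as covariates should say where they enter the analysis, and this one does not. Emetic potential is part of the eligibility rule and varies among eligible patients, so the regimen is an obvious candidate to explain differences in nausea. With 33 per arm and no stated stratification, the arms can differ noticeably on such a factor by chance.

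Phase II exists to estimate an effect size. The realised estimate is therefore the main product, and its accuracy given the imbalance that occurs matters. Variance that recorded baseline data could explain stays in the error term. A covariate list with no rule for its use also leaves the choice of adjustment open until the data are seen.

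**Working it through.** **Inputs from the documents (Sample size and statistical power).** "a standard deviation of 2.44"; "a clinically meaningful difference in mean nausea severity score of one"; and "with 90% power, the required sample size is 33 participants for each group". The target standardised effect is 1/2.44 = 0.41. Alpha is not stated; two-sided 0.05 is assumed.

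**Assumed inputs.** The documents give no share of patients on severe-potential regimens, no score gap between emetic classes, and no R² for any covariate. The illustration uses a share of 30% to 50% and a gap of 1 to 2 points.

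**1. The plan's own figure.** n per arm = 2(1.960 + 1.282)² × 2.44² / 1² ≈ 125.1, so 126, not 33. At 33 per arm the power is 38% (normal approximation; 37.5% by exact t). The stated size is not reproduced, so precision is scarcer than the plan assumes.

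**2. Chance imbalance at 33 per arm (exact binomial, independent arms).** A gap of 15 points or more means at least 5 patients (5/33 = 15.2 points). A gap of 20 points or more means at least 7 (7/33 = 21.2 points).

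| Assumed share | SD of difference | P(15 points or more) | P(20 points or more) |
|---|---|---|---|
| 30% | 0.113 | 0.23 | 0.08 |
| 50% | 0.123 | 0.27 | 0.11 |

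**3. Effect on the realised difference.** Shift = score gap × imbalance. For a 20-point imbalance:

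- gap of 1 point: 1 × 0.20 = 0.2 points, or 0.2/2.44 = 0.08 in d
- gap of 2 points: 2 × 0.20 = 0.4 points, or 0.4/2.44 = 0.16 in d

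The target is 1 point (d = 0.41). The unadjusted standard error is 2.44 × √(2/33) = 0.60 points, so these shifts are one third to two thirds of a standard error.

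**4. Variance explained.** R² = p(1 − p) × gap² / 2.44², with 2.44² = 5.95.

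- p = 0.5: 0.25/5.95 = 0.042 at 1 point; 1.00/5.95 = 0.168 at 2 points
- p = 0.3: 0.21/5.95 = 0.035 at 1 point; 0.84/5.95 = 0.141 at 2 points

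At p = 0.5 the equivalent gain in patients is 1/(1 − R²) = 1.04 to 1.20.

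**5. Simulation (20,000 runs per setting, 33 per arm, true difference 1, three covariates with equal contributions).** Both estimators average about 1.00.

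| Total R² (assumed) | SD, unadjusted | SD, adjusted | Power, unadjusted | Power, adjusted |
|---|---|---|---|---|
| 0.1 | 0.60 | 0.58 | 37% | 39% |
| 0.2 | 0.60 | 0.55 | 37% | 43% |
| 0.3 | 0.60 | 0.52 | 37% | 49% |

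Adjustment helps, but at none of these values does it approach 90% power.

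**The case against.** Under 1:1 randomization the unadjusted test is valid and the estimate is unbiased. Chance imbalance is already part of its standard error, and the interval for d is wide in any case (about ±0.49). Imbalance and unexplained variance are largely one loss described in two ways. All of this stands. A reader might infer that the planned effect size is biased; the documents do not support that, and the simulation shows no average bias.

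A reader might also infer that the plan rules out adjustment everywhere. That is too strong. The t-test, Wilcoxon test, raw d and ANOVA are described without covariates, but the longitudinal model is only loosely specified. It is unadjusted by omission, and the heading Co-variates suggests some intended use.

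The size is illustrative. A 50% share is the value most prone to imbalance, which is why 30% is shown beside it. A gap above 2 points would give larger figures, but nothing in the documents supports one. Age, sex and the self-management count are not quantified separately. T1 severity may also predict weakly, because it is measured before the first chemotherapy and covers the preceding week.

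What survives is that the plan does not say which recorded covariates enter which model, although using them costs little.

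**Conclusion.** The point holds as a matter of precision and prespecification. Factors the plan itself expects to influence CINV, and T1 severity, are collected before randomization but are used in no specified between-group analysis and in no stated stratification.

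On an assumed share of 30% to 50% and an assumed gap of 1 to 2 points, an imbalance of 15 points or more has probability 0.23 to 0.27. A 20-point imbalance moves the difference by 0.2 to 0.4 points against a 1-point target. Adjustment for that factor removes about 4% to 17% of the variance at 50% prevalence, slightly less at 30%. The finding does not show that the unadjusted analysis is invalid. Nor should adjustment be read as a rescue of the stated 90% power: that shortfall is a separate and larger problem.

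**What to change.** **N/V severity.** Make the primary analysis a longitudinal model over T2 to T4 with arm, time and arm-by-time, adjusted for T1 severity, emetic class, age (continuous) and sex. Name the primary contrast in advance, for example the arm difference averaged over T2 to T4. Derive emetic class (moderate or severe) from the regimen planned before allocation, by a written rule fixed before unblinding; it is not a named variable now. Use no covariate recorded after randomization.

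**Self-management behaviors.** Use a count model, for example a negative binomial GEE, with the same covariates except T1 severity; Table 3 gives the count itself no T1 value.

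**Reporting.** Give the adjusted difference for severity and the rate ratio for the count, each with a 95% CI. Define the standardised effect for severity as the adjusted difference divided by the unadjusted pooled SD. Dividing by the residual SD would inflate it: at R² = 0.168, 1/(2.44 × √0.832) = 0.45 instead of 0.41. Keep the t-test or Wilcoxon results and raw d as supportive.

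**Cost.** SAP wording, modest programming, the classification rule and about four degrees of freedom. The data are already planned, so there is no added patient burden.

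### The over-time test named for the group comparison in AIM 2 is a one-way repeated measures ANOVA, which in standard meaning has no group term, and the role of baseline severity is not stated

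*Combined protocol and SAP*

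**What the plan says.** All references are to the combined protocol and SAP.

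- **Data Analysis, Phase II, AIM 2.** The aim covers differences "between, and within, the intervention and attention control groups". For the primary endpoints, "the method of analysis of longitudinal data will be used to compare the difference between intervention and control groups over time"; the model is not named. "The generalized estimating equation (GEE) approach may be used to enhance the robustness of the estimation of model parameters", on condition that the working correlation is hard to fix in advance. "In the longitudinal model treatment cycle time, interaction of time and treatment, or both, whenever feasible, may be added into the model". Then comes the sentence at issue: "The one-way repeated measures ANOVA will be used to assess the difference between the two groups". A further option is listed after it: "The mixed effect model may be used as exploratory analysis". Finally, "comparisons between two groups at each treatment cycle time point will be performed for all primary and secondary endpoints".
- **Principle data analysis.** The primary endpoints are the nausea/vomiting severity score and the number of self-management behaviors. The test at each cycle is a t-test, or a Wilcoxon rank-sum test if normality cannot be confirmed.
- **Recruitment and randomization; Table 3.** "Eligible patients will be approached by the RN at their first chemotherapy appointment and asked to participate". Baseline measures come after consent and before randomization. Severity is collected at T1 to T4, and self-management behaviors at T2 to T4 only.
- **Co-variates.** The list of T1 characteristics does not include T1 severity. No section says whether T1 severity is a covariate, a repeated outcome or left out.

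**The concern.** The only repeated-measures method that is both named and committed is the ANOVA. Its standard form fits the within-group part of AIM 2, yet the sentence assigns it to the between-group part. An analyst who follows the label would report a test of time as if it were a test of group. It could be significant when the arms do not differ and could miss a real difference.

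T1 severity matters because the intervention cannot have affected it. If it enters as one more outcome visit, without a group-by-cycle term, it pulls the estimated effect toward zero. If it enters as a covariate, it may sharpen the comparison. With this left open, the choice could be made after the data are seen.

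**Working it through.** **Inputs.** From Sample size and statistical power: 33 per group, SD 2.44, difference 1 point. Not in the documents and assumed here: two-sided alpha 0.05, equal correlation between visits (0.5, range 0.3 to 0.7), equal SD at T2 to T4, and the T1 SD.

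**The plan's own figure.** The plan states no operating characteristic for the ANOVA or the longitudinal model. Its 33 per group at 90% power does not follow from the usual two-group formula: 2 × 2.44² × (1.960 + 1.282)² / 1² = 125.1, so 126 per group, and 33 per group gives 38% power. That is a separate matter. The powers below serve only to compare ways of handling T1.

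**Step 1. The ANOVA taken literally.** With cycle as the only factor and n = 66 patients pooled, the F test for cycle has noncentrality n × S / (SD² × (1 − correlation)), where S is the sum of squared deviations of the pooled cycle means from their average.

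- *T2 to T4, constant group difference of 1 or 2 points, no time trend.* Pooled cycle means are equal, so S = 0. The group difference is absorbed into the patient effects. Rejection stays at alpha; simulation (20,000 trials) gives 5.0% and 5.3%. A t-test on patient means detects the 1-point difference in about 52%.
- *T2 to T4, no group difference, both arms drift 0, 0.5, 1.* S = 0.25 + 0 + 0.25 = 0.5. Noncentrality = 66 × 0.5 / (5.954 × 0.5) = 11.1 on 2 and 130 df, giving about 85%; simulation 84%.
- *T1 to T4, no group difference, both arms rise 1 point after T1.* S = 0.75² + 3 × 0.25² = 0.75. Noncentrality 16.6 on 3 and 195 df, giving 94%; simulation 94% (83% to 99.6% for correlation 0.3 to 0.7).
- *T1 to T4, control arm flat, 1-point group difference after T1.* Simulation 35% (27% to 56%). The test reacts only because the pooled mean moves.

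**Step 2. T1 as an outcome without a group-by-cycle term, equal visit weights.** The effect is (0 + 1 + 1 + 1)/4 = 0.75. Power = Φ(effect / (SD of patient summary × √(2/33)) − 1.96), with √(2/33) = 0.2462. Correlation among T2 to T4 is 0.5.

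- T2 to T4 only: SD = 2.44 × √((1 + 2 × 0.5)/3) = 1.992; 1/(1.992 × 0.2462) = 2.04; power 53%.
- T2 to T4 adjusted for T1 at correlation 0.5: SD = 2.44 × √(2/3 − 0.25) = 1.575; power 73%.
- T1 pooled in, T1 SD 2.44, correlation 0.5: SD = 2.44 × √(2.5/4) = 1.929; power 35%.

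| T1 assumption | T1 pooled in | T2–T4 only | T2–T4 adjusted for T1 |
|---|---|---|---|
| SD 2.44, correlation 0.5 | 35% | 53% | 73% |
| SD 1, correlation 0.5 | 45% | 53% | 73% |
| SD 2.44, uncorrelated | 47% | 53% | 53% |
| SD 1, uncorrelated | 52% | 53% | 53% |
| SD 0 | 53% | 53% | 53% |

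**Step 3. The same pooling, with visits weighted by their variance.** Take T1 SD 1, uncorrelated with later cycles. The variance of the T2 to T4 mean is 1.992² = 3.97. The weight on T1 is 1/(1 + 1/3.97) = 0.80, so the effect is 0.20 of its T2 to T4 value. The SD of the weighted mean is √(1/(1 + 1/3.97)) = 0.894. Power = Φ(0.201/(0.894 × 0.2462) − 1.96) = 15%. Low, narrow T1 scores are therefore close to harmless under equal weights (52%) but not under variance weights.

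**The case against.** The strongest reply is that the sentence states its own purpose. A time-only ANOVA gives no group estimate, so an analyst would notice, and one-way may loosely count the single between-patient factor. The rest of AIM 2 supports this: it commits to comparing groups over time, the option to add a time-by-treatment term presupposes that treatment is already in the model, and t or Wilcoxon tests at each cycle are promised for all primary and secondary endpoints. This largely stands. A reader might infer that the trial has no valid group test, or that its false-positive rate will be 84%. The documents support neither: valid tests are committed, and the rejection rates apply only if the label is followed literally.

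A second reply is that the size of the T1 problem is unknown. That also stands. A reader might take 35% against 73% as the established loss, but it needs a T1 SD and a correlation that the documents do not give, and a model without the interaction that the plan lists as an option. The opposite inference, that narrow T1 scores make the choice harmless, fails too, as Step 3 shows.

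A third reply is that Phase II aims first to estimate effect size, and Cohen's d under AIM 1 does not depend on the ANOVA. This softens the point. But AIM 2 is still a group comparison on declared primary endpoints. On their own, the unnamed estimator and contrast are mostly missing detail.

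**Conclusion.** Should be fixed. The named over-time test does not, in its standard meaning, do the job assigned to it, and the handling of a pre-randomization measure of a primary endpoint is left open. Confidence is high on the wording and the omission, and lower on size.

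On the literal reading, with correlation 0.5, the ANOVA over T2 to T4 rejects in about 5% of trials for a real constant difference and in about 84% for a shared drift with no difference. Pooling T1 without an interaction leaves 75% of the effect under equal weights and about 20%, with power about 15%, in the variance-weighted case of T1 SD 1 and no correlation. The T1 SD and the correlation behind these figures are assumptions.

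**What to change.** Replace the ANOVA sentence with one model and one contrast for each primary endpoint.

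- **Severity.** A repeated-measures mixed model on T2, T3 and T4 with group, cycle, group-by-cycle and T1 severity as a covariate. Primary contrast: the group difference averaged equally over T2 to T4, with 95% CI.
- **Number of self-management behaviors.** There is no T1 value, so the same baseline-adjusted model cannot serve. Use GEE on T2 to T4 with group, cycle and group-by-cycle and a log link for counts. Primary contrast: the rate ratio averaged over T2 to T4, with 95% CI.
- **Other parts of AIM 2.** Read within-arm change over cycles from the same models. Label the t or Wilcoxon tests at each cycle as supportive.

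This changes analysis wording only, with no new data or visits, and both model types are already listed in the plan. The price is committing to one model and one contrast in advance. If T1 scores prove nearly constant, the adjustment brings little gain and little harm.

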Recruitment of CAB: Sampling will be purposive. The CAB will consist of 5 older adults who have finished cancer treatment with chemotherapy within the past 3 years, 3 family caregivers, and 2 oncology staff nurses who deliver chemotherapy treatments. Older adults and caregivers are the critical voice of the target audience, and oncology trained nurses are important to verify accuracy of recommended CINV self-management strategies within the game and current treatment center discharge instructions. To the greatest extent possible, all CAB members will be present at each focus group. CAB members will provide input for scenarios (incidence, self-management, perceived and actual consequences) based on their experiences with CINV. Older adults will be recruited from a pool of approximately 109 participants from the PIs prior research studies who agreed to be contacted for further research.

Names will be randomly drawn from this pool; an invitation to participate will be mailed in batches of 10

Figure 3: Principles of Serious Gaming

- Knowledge sets stage for behavioral change
- Practicing skills leads to self-mastery
- Modeling is an effective way to learn new skills
- Tailored games facilitate character identification
- Game must be entertaining

until target numbers are reached. Nurses will be recruited from the UF Health Cancer Center-Orlando chemotherapy treatment center. Retention will be enhanced by offering a \$50 stipend/gift card to the CAB members for each focus group they participate in. Informed consent and participant characteristics (e.g., age, gender, race, educational level, CINV experience) information will be collected from all CAB members.

Phase II - Game prototype testing

Phase II will use a prospective 2-group randomized, longitudinal design to evaluate effect size of the intervention, examine group differences and evaluate game appeal. Patients who meet the inclusion criteria will be randomly assigned into the intervention group or control group at a 1:1 ratio. All participants will be followed for four chemotherapy cycles (approximately 4 months).

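### The sample size of 33 per group does not give 90% power for a one-point difference: the stated inputs give about 37%, and 33 per group fits a two-point difference

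*Combined protocol and SAP*

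**What the plan says.** In the combined protocol and SAP, the section headed Sample size and statistical power takes "a nausea severity mean score of 6.20, range from 2 to 9", with "a standard deviation of 2.44" and "a clinically meaningful difference in mean nausea severity score of one between the intervention and control groups". From these it concludes that "with 90% power, the required sample size is 33 participants for each group, yielding a total sample size of 66 for the study". It gives no alpha, sidedness, test, within-patient correlation or number of repeated measurements.

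The Phase II introduction says that patients are "randomly assigned into the intervention group or control group at a 1:1 ratio". The Sample size paragraph under Phase II says "Sixty-six participants will be enrolled" and closes with "We will oversample by 20% in order to account for attrition".

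The Data Analysis section names the nausea/vomiting severity score as one of two primary endpoints. It plans a t-test or Wilcoxon rank-sum test between groups at each cycle, together with longitudinal models.

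**The concern.** A one-point difference against an SD of 2.44 is a standardised effect of about 0.41. Thirty-three per group is far too few to detect an effect of that size with 90% power, so the paragraph looks internally inconsistent.

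The trial claims high power for the effect that it calls clinically meaningful, on a primary endpoint. A reader who trusts the claim could take a null result as good evidence against a one-point benefit. On the stated inputs, a single-cycle comparison would miss such a benefit more often than it would find it.

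A second inconsistency compounds this. The same 66 serves as the number required and the number enrolled, and 20% oversampling is also promised.

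**Working it through.** **Inputs.** Difference 1 point, SD 2.44, power 90% and 33 per group come from Sample size and statistical power. The 1:1 allocation comes from the Phase II introduction, and the t-test from the Data Analysis section. Alpha is not stated, so two-sided 0.05 is assumed and varied below. The mean of 6.20 and the range of 2 to 9 do not enter a comparison of two means.

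**1. Trying to reproduce 33 per group.** The normal approximation is n per group = 2(z₀.₉₇₅ + z₀.₉₀)² × SD² / difference².

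- (1.960 + 1.282)² = 10.507, and 2.44² = 5.954.
- n = 2 × 10.507 × 5.954 / 1² = 125.1, so 126 per group.
- The exact t-test (noncentral t) gives 126.1, so 127 per group and 254 in total.

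The plan's figure does not reproduce. It is about a quarter of what its own inputs require.

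**2. Power at 33 per group for one point.** The noncentrality is 1 / (2.44 × √(2/33)) = 1.665, on 64 degrees of freedom.

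| Alpha | Power (t-test) |
|---|---|
| two-sided 0.05 | 37% |
| two-sided 0.10 | 50% |
| two-sided 0.20 | 65% |
| one-sided 0.05 | 50% |
| one-sided 0.10 | 65% |

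Reaching 90% would take a two-sided alpha of about 0.64 with rejections in both tails counted, or about 0.70 with the correct tail only.

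**3. Which inputs do give 33?**

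- Difference 2, SD 2.44: the normal approximation gives 125.1 / 4 = 31.3, so 32. The t-test gives 32.3, so exactly 33, with 90.6% power.
- Difference 1, SD about 1.23: 33 per group has 90% power. This is the same standardised effect, reached by roughly halving the SD.
- The smallest difference detectable with 90% power at 33 per group and SD 2.44 is 1.98 points.
- Other misreadings do not reach 33 (normal approximation, two-sided 0.05): 2.44 read as a variance gives 52, a one-sample or paired formula gives 63, and an SD of range/4 = 1.75 gives 65.

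**4. Could the repeated measurements explain it?** Table 3 shows three post-baseline assessments (cycles 2, 3 and 4). With a common correlation ρ, the variance of their mean is SD² × (1 + 2ρ)/3. Adjusting for baseline with the same correlation subtracts ρ² from that factor. Power at 33 per group for one point (t-test, two-sided 0.05) is:

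| ρ | Mean of 3 cycles | Mean of 3, baseline-adjusted |
|---|---|---|
| 0 | 81% | 81% |
| 0.3 | 61% | 69% |
| 0.5 | 52% | 72% |
| 0.75 | 44% | 88% |
| 0.8 | 42% | 93% |

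Four uncorrelated measurements would give 91%. However, the first of the four is the baseline, taken before randomisation, so it cannot carry a treatment effect.

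**5. Enrolment.**

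- If 66 are enrolled and 20% are lost: 66 × 0.8 = 52.8, about 53 (26 and 27 per group). Power is 31% for one point and 83% for two.
- If 66 is the evaluable target: 66 / 0.8 = 82.5, so 83 enrolled.
- If 20% is added to 66: 66 × 1.2 = 79.2, so 80 enrolled. After a 20% loss, 80 × 0.8 = 64 remain (32 per group), with 36% power for one point and just under 90% for two.

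**The case against.** **The planned analysis is longitudinal, so 37% may be too pessimistic.** This is partly right. The 37% describes a two-group comparison at a single cycle, and a baseline-adjusted mean of the three later cycles could exceed 90% if the correlation were near 0.8. But the sample size paragraph states no correlation, no number of measurements and no baseline adjustment. A correlation that high would need justification, because the baseline is taken before the first chemotherapy. The plan cannot rest its figure on assumptions that it does not make.

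**A two-point target is an inference.** This stands. The documents nowhere mention two points, and a halved SD fits about as well. The arithmetic shows that the inputs conflict, not which one is wrong.

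**The oversampling sentence may mean that about 80 will be enrolled.** That is a possible reading, so the figures for 53 completers are conditional on 66 being the enrolled number. The text still supports more than one enrolment total.

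**Phase II is mainly about estimating an effect size and feasibility.** Those are stated aims, and a pilot may be small. But Aim 2 compares the groups, severity is a primary endpoint, and the plan makes an explicit 90% power claim. How a null result would be read is a matter of judgement. That the claim is wrong is not.

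**Conclusion.** The concern holds. With SD 2.44 and a one-point difference, 33 per group has about 37% power, not 90%, and 90% power needs 127 per group. This rests on a two-sample t-test at a single cycle and two-sided alpha 0.05, which the plan does not state. No conventional alpha changes the conclusion. Averaging the three post-baseline cycles without baseline adjustment reaches 81% at most, and only if the cycles are uncorrelated. The stated size matches a standardised effect of about 0.82, twice the one stated. Separately, the enrolment figure is ambiguous. If 66 is the number enrolled and 20% are lost, even a two-point difference has only 83% power. The power statement must be corrected.

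**What to change.** The sponsor should say which input is in error (difference, SD, power or size) and restate the calculation with alpha and sidedness so that the figures agree. Two consistent forms, both at two-sided 0.05 with SD 2.44 and 33 evaluable per group, are:

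- a two-point difference with 90% power, adding that power for one point is about 37%. This form also needs a reason why two points is the relevant target;
- the one-point difference kept, with power stated as about 37% and the effect-size aim given as the reason for the size.

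If the sponsor means to rely on the longitudinal analysis, the paragraph should state the model, the number of measurements and the assumed correlation, with its source.

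Give one enrolment figure and the evaluable number it leaves after 20% loss: 83 enrolled for 66 evaluable, 80 enrolled for 64, or 66 enrolled for about 53, with the power at that number.

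The cost is wording in the two sample size paragraphs. Restating the power figures needs no extra patients beyond the oversampling already promised, but the stated power or detectable difference becomes less favourable.
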